- b. The modified intent-to-treat (mITT) population includes all subjects who meet all inclusion/exclusion criteria, apply at least one (1) dose and return for at least one (1) post-baseline evaluation visit.
- c. The safety population (intent-to-treat (ITT)) includes all subjects who meet all inclusion/exclusion criteria and apply at least one (1) dose.

21. ENDPOINTS:

a. Clinician Reported Outcome (ClinRO) - Anoscopy (Visits 2, 4).

Anoscopy – Visual assessment of hemorrhoids (Fukuda et al. 2005; Lunniss and Mann 2004). Video of the procedure will be recorded for blinded central reading and assessment according to the following scale:

Swelling	% Lumen	Score	
	0	None	0
	≤25	Mild 1	
	≤50	Moderate 2	
	≤75	Severe	3
	>75	Very severe	4

b. Patient Reported Outcome (PRO) – Internal Hemorrhoid Sign and Symptom Assessment (IHSSA) (Daily between Visits 1 and 5).

Corporate Information

Corporate Information

post-bowel movement assessment, and end of day assessment are included in **Appendix 1**.

c. Patient Reported Outcome (PRO) – Patient Reported Outcome Measurement Information System (PROMIS) Global Health Questionnaire Version 1.2 (Visits 2 and 4).

The PROMIS Global Health Questionnaire is completed by patients during Visits 2 and 4. It will be completed before any clinical or laboratory tests are administered. The PROMIS Global Health Questionnaire assesses an individual's physical, mental, and social health using 10 items. The measure is generic, rather than disease-specific, and often uses an "In General" item context as it is intended to globally reflect individuals' assessment of their health. The questionnaire produces two scores: Physical Health and Mental Health. Raw scores for both scales are converted to T-scores with a mean of 50 and standard deviation of 10. The items of the PROMIS Global Health Questionnaire are included in **Appendix 2**.

d. Patient Reported Outcome (PRO) – Patient Global Impression of Severity (Visits 2 and 4) and Patient Global Impression of Change (Visit 4) Items

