The Patient Global Impression of Severity (PGIS) and Patient Global Impression of Change (PGIC) items are designed to capture the patient's overall perspective on sign and symptom severity. The 8-item PGIS asks patients to rate the severity of their hemorrhoid-related signs and symptoms over the past week. The 9-item PGIC asks patients to rate the direction and magnitude of the change in their signs and symptoms since starting the study medication. The PGIS and PGIC are included in the study to help establish the threshold for clinically relevant change on the IHSSA. Although they address signs and symptoms of internal hemorrhoids, the IHSSA is considered the primary measure of these constructs. The PGIS and PGIC items are included in **Appendix 3**.

Based on the results of the pilot study, primary and secondary endpoints will be selected for future studies.

22. SUBJECT SAFETY:

a. Safety assessment will be conducted on all subjects administered at least one suppository. Adverse drug reactions may include burning and local irritation upon application. Systemic absorption of topical corticosteroids has produced reversible suppression of the HPA axis. Adverse medical events experienced by the subjects will be tabulated. The relationship of adverse events, if any, to the study drug will be assessed by the Investigator (see Section 24).

26Apr2019 Protocol: **HDCS 1701** Page 14 of 67

b. Physical Examination

The investigator, sub-investigator or appropriately delegated designee, (Physician's Assistant, Advanced Registered Nurse Practitioner, and Registered Nurse as per local regulations) will perform a brief physical examination, prior to the Subject starting study drug.

The physical examination will include, at a minimum, examination of the Subject's general appearance, skin, HEENT (head, eyes, ears, nose and throat), heart, lungs, musculoskeletal system, neurological system, lymph nodes, abdomen and extremities.

Vital signs, including blood pressure, pulse rate, respiratory rate and oral body temperature will be documented at Visit 1. Vital signs will be measured after the Subject has rested in a seated position for at least 5 minutes.

The Subject's body weight will also be measured while the Subject is lightly clothed (e.g., no coat or shoes). Height will be measured without shoes.

c. Concomitant medications

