- ix. Obtaining additional tests to evaluate liver function, as appropriate (e.g., INR, direct
- Considering gastroenterology or hepatology consultations. X.

f. Pilot study stopping criteria

The pilot study may be stopped if ≥2 patients on drug develop the same CTCAE v4.0 Grade 3 adverse event or if 1 patient develops a CTCAE v4.0 Grade 4 or higher adverse event (Appendix 4).

23. STATISTICAL METHODS:

Endpoints

Anoscopy results at Day 15 will be compared to responses at baseline (Day 1). IHSSA scores from Days 1-15 (treatment period) and 16-29 (follow-up period) will be compared to responses from Days -14 to -1 (baseline period). The 95% confidence intervals for the differences between the change from baseline for the hydrocortisone acetate suppository and that for the placebo will be calculated.

b. Safety

The incidence of all AEs reported during the study will be classified based on Medical Dictionary for Regulatory Activities (MedDRA) version 21.0 terminology (system organ classes and preferred terms) and summarized for each treatment group. Incidence of adverse events will be tabulated by system organ class, preferred term, and severity, and by system organ class, preferred term, and relationship to study drug.

24. ADVERSE EVENTS:

Definitions

- Any untoward events occurring during the study will be documented and summarized upon completion of the study.
- The term Adverse Event (AE) will cover any untoward medical occurrence in a clinical investigation where a volunteer was administered an investigational product, which does not necessarily have to have causal relationship with this treatment. An adverse event can therefore be any unfavorable and unintended sign (including clinically significant abnormal laboratory finding, for example), symptom, or disease temporally associated with use of a medicinal product, whether considered related to the medicinal product. This includes all events both expected and unexpected (the nature or severity of which is not consistent with information in the relevant source document(s)).

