- iv. Definite: The AE occurs following the application of the study drug and it cannot be reasonably explained by any known characteristics of the Subject's clinical state, environmental or toxic factors or other modes of therapy administered to the Subject. It disappears or decreases upon discontinuation of the study drug and reappears on a re-challenge of the investigational product.
- g. Documentation and Reporting of Adverse Events
 - i. For the purposes of this study, the period of observation of adverse events extends from the start of treatment with the investigational product until the final study visit. During this period, all adverse events spontaneously reported by the volunteer, observed by the Qualified Investigator (or delegates) or elicited by general questioning will be documented in the CRF and will be reported in the final report.
- ii. If necessary, every effort will be made to obtain an adequate follow-up of the volunteers. Should any volunteers choose to withdraw early from the study, they will be advised of the safety precautions to be taken.
- iii. The volunteers will be questioned on their health status at the beginning of the study and before their departure from the clinical site. An open-ended question will be asked.
- iv. It is the qualified investigator's responsibility to record and report all adverse events that occur during the study regardless of their relationship to the study medication. If judged necessary by the qualified investigator, an adverse event will be reported in accordance with the applicable regulatory requirements.
- h. Pregnancy in a female volunteer on the study shall be reported to the sponsor or their authorized representative within 24 hours of the knowledge of its occurrence by the qualified investigator that such pregnancy occurs during the Study or right after. Because of the possibility that the fetus/embryo could have been exposed to the study drug through the parent and for the volunteer's safety, the pregnancy will be followed up to determine outcome as, including spontaneous or voluntary termination, details of birth, presence or absence of any birth defects, congenital anomalies, or maternal and/or newborn complications.

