- 7. Blood and urine samples will be collected for clinical laboratory tests including complete blood count (CBC), comprehensive metabolic panel (CMP), urinalysis, HIV, Hepatitis B, and Hepatitis C, and drug screening (drugs of abuse, prescription).
- 8. A breath alcohol test will be conducted.
- 9. When the Subject has completed all screening procedures, compliance with the inclusion and exclusion criteria will be reviewed. (See Sections 12 & 13 Inclusion & Exclusion Criteria)
- 10. The following will be dispensed during Visit 1:
 - A diary card to record Adverse Events and Concomitant Medications along with instructions on how to complete.
 - Backup diary cards to record missed ePRO questionnaires (as needed)
- 11. Appropriate study personnel will provide training to the Subjects on Internal Hemorrhoids Sign and Symptom Assessment (IHSSA) and ePRO, which will be recorded by the Subjects daily during the study. (See Appendix 1)
- 12. Cognitive interviews will be conducted with selected Subjects via a third party to discuss IHSSA and internal hemorrhoid signs and symptoms of the Subjects. (See Section 27. Subject Interviews)
- 13. Visit 2 (Day 1, 14±2 days from Visit 1) will be scheduled and the Subject will be instructed to bring the Subject diary and backup ePRO diary (if applicable) with him or her to this visit.

2. Visit 2: Start of Treatment (Day 1)

The following procedures will be performed at Visit 2:

- 1. The overall status of the Subject's internal hemorrhoids will be assessed using the PGIS (ePRO). (See Appendix 3)
- 2. The Subject's symptomatic internal hemorrhoid will be assessed by an anoscopic examination (Grade I, II or III (Banov et al. 1985)). (See Section 16 Diagnostic Tests) To be included in the study, subjects must have a diagnosis of symptomatic Grade I, II or III internal hemorrhoids. Video of the procedure will be recorded for blinded central reading and assessment of swelling as the Clinician Reported Outcome (ClinRO).

26Apr2019 Protocol: **HDCS 1701** Page 26 of 67

- 3. Appropriate study personnel will review the use of IHSSA with the Subject. (See Appendix 1)
- 4. The use of concomitant medications since the previous study visit will be documented and assessed for each Subject. (See Section 22. Subject Safety)
- 5. The occurrence of all AEs will be assessed and documented following procedures in Section 24 Adverse Events.
- 6. A urine pregnancy test will be conducted for all female Subjects of childbearing potential.

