- 7. When the Subject has completed all screening procedures, compliance with the inclusion and exclusion criteria will be reviewed. (See Sections 12 & 13 Inclusion & Exclusion Criteria) After the inclusion and exclusion criteria have been confirmed, the Subject will be randomized to a treatment group. The Subject will be assigned a randomization number (See Section 11. Randomization).
- 8. The following will be dispensed during Visit 2:
 - The Investigational Product (28 suppositories)
 - A diary card to record IP Use, Adverse Events and Concomitant Medications along with instructions on how to complete.
 - Backup diary cards to record missed ePRO questionnaires (as needed)
- 9. Randomized Subjects will be instructed on the correct method for the application of the Investigational Product. The first application of the Investigational Product will be performed by the Subject at home. The study restrictions will also be reviewed with the Subject and an instruction sheet will be issued to the Subject. (See Section 14. Treatments)
- 10. Randomized Subjects will be instructed how and when to complete the diary for Study Medication use. They will be told that they are to document all treatments administered, including the date and all treatments missed. In addition, Subjects will be reminded to document all AEs. Subjects will also be instructed to call the study site if they experience any severe intolerability to Investigational Product.
- 11. PROMIS Global Health questionnaire will be performed.
- 12. Study instructions will be reviewed with the Subject, including the procedure for application of the Investigational Product. (See Section 14. Treatments)
- 13. Visit 3 (Day 8 ± 1 days from the date of Visit 2) will be scheduled and the Subject will be instructed to bring the Subject's diary and backup ePRO diary (if applicable) with him or her to this visit.

3. Visit 3: Interim Visit (Day 8±1)

The following procedures will be performed at Visit 3:

- 1. Appropriate study personnel will review the use of IHSSA with the Subject. (See Appendix 1)
- 2. The use of concomitant medications since the previous study visit will be documented and assessed for each Subject. (See Section 22. Subject Safety)
- 3. A urine pregnancy test will be conducted for all female Subjects of childbearing potential.
- 4. Blood sample will be collected from the Subject for clinical laboratory tests: comprehensive metabolic panel (CMP).

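### Section 20.c restricts the safety population to eligible dosed subjects, Section 22.a assesses safety in every dosed subject, and the ITT label on 20.c does not fit the set it names

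*Combined protocol and SAP*

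**What the plan says.** Section 20.c gives the protocol's only definition of a safety population: "The safety population (intent-to-treat (ITT)) includes all subjects who meet all inclusion/exclusion criteria and apply at least one (1) dose". Membership needs both eligibility and dosing, and the set is labelled ITT.

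Section 22.a describes the safety assessment differently: "Safety assessment will be conducted on all subjects administered at least one suppository". The same paragraph adds: "Adverse medical events experienced by the subjects will be tabulated". Neither sentence mentions eligibility.

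Section 23.b, the safety analysis section, begins: "The incidence of all AEs reported during the study will be classified". It then asks for summaries by treatment group but names no analysis population. Section 24.g.i says that adverse events in the observation period, whether reported spontaneously, observed or "elicited by general questioning will be documented in the CRF and will be reported in the final report". It does not define a population either.

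Two procedural statements in Section 28 bear on how often the definitions can differ. At Visit 2, item 7: "After the inclusion and exclusion criteria have been confirmed, the Subject will be randomized to a treatment group". At Visit 2, item 9: "The first application of the Investigational Product will be performed by the Subject at home".

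**The concern.** A subject is informative about safety because of exposure to the drug, not because of meeting the entry criteria. If 20.c is followed as written, anyone who took a suppository and was later found not to have met a criterion drops out of the adverse event tables. If 22.a is followed, that person stays in. The programmer has two current sections that disagree and an analysis section that is silent.

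Several exclusion criteria in Section 13 relate to safety: known allergy to hydrocortisone or listed ingredients, immunocompromise, and glucocorticoid use within 2 months. Subjects who slip past those criteria may be the ones whose events matter most. Safety and tolerability is one of the two objectives in Section 3, and with about 50 subjects per arm a single event is visible in a table.

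The label is a second, smaller problem. A reader who meets ITT will take it to mean all randomized subjects, and 20.c does not describe that set.

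**Working it through.** There is no figure in the plan to reproduce, so the check is a comparison of the definitions followed by an illustration.

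**Who is in which set**

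| Subject | 20.c safety (ITT) | 22.a safety assessment | All randomized |
|---|---|---|---|
| Randomized, eligible, dosed | in | in | in |
| Randomized, dosed, later found ineligible | **out** | **in** | in |
| Randomized, never dosed | out | out | **in** |

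The second row is the conflict between 20.c and 22.a. The second and third rows show why ITT is the wrong name for 20.c. The third row can occur because randomization takes place at Visit 2 and the first dose is taken later at home. No section defines a set of all randomized subjects. The 20.c set differs from the mITT set in 20.b only by not requiring a post-baseline visit.

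Sections 23.b and 24.g.i refer to all adverse events without an eligibility condition. They sit more easily with 22.a, but because neither defines a population they conflict with 20.c only by implication.

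**Can ineligibility surface after dosing?** The entry checks make it uncommon. Section 28 says for Visit 1 (item 9), and repeats for Visit 2 (item 7): "When the Subject has completed all screening procedures, compliance with the inclusion and exclusion criteria will be reviewed". Randomization follows only after confirmation. Late discovery remains possible:

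- Under Section 26.d, source documents include the evidence for the diagnosis, and monitors validate CRF data against source at visits that can follow dosing.
- Inclusion criteria 12.a and 12.b are computed from two weeks of diary data, with paper backups for missed electronic entries (Section 18), so later reconciliation could change whether a threshold was met.

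**Size for one excluded subject.** Inputs: 50 per arm (Section 8). Assumed: one dosed subject in the arm found ineligible, and one event in the arm. Intervals are exact Clopper-Pearson 95%.

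- All dosed subjects (22.a): 1/50 = 2.0% (0.05–10.65%).
- 20.c, when the excluded subject had the event: 0/49 = 0% (0–7.25%).
- 20.c, when another subject had the event: 1/49 = 2.04% (0.05–10.85%).

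If exclusion is unrelated to the event, the chance that the single event belongs to the excluded subject is 1/50 = 2%. If exclusion is related to risk, that figure need not apply.

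**How often the sets could differ.** The documents give no rate of ineligibility found after dosing. With about 100 dosed subjects and an assumed independent rate q per subject, P(at least one) = 1 − (1 − q)^100:

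- q = 1%: 1 − 0.99^100 ≈ 63%
- q = 2%: 1 − 0.98^100 ≈ 87%
- q = 5%: 1 − 0.95^100 ≈ 99%

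These are chances that the two sets differ by at least one subject, not that a safety conclusion changes.

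**The case against.** The strongest reply is that the operative safety text already gives the right result. Section 22.a covers all dosed subjects, 23.b speaks of all reported events, and no later section invokes the 20.c set. A statistician working from Sections 22 and 23 would tabulate everyone dosed. This supports reading all dosed subjects as the intent, but it does not remove the conflict: 20.c is the only section that defines a safety population, and no passage says that 22.a prevails over it.

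It can also be said that no event is lost. Section 24.g requires all events to be recorded and reported, serious events are reported without regard to analysis population, and the withdrawal and stopping rules in 22.e and 22.f do not depend on 20.c. That stands. What is at stake is the incidence table, meaning its numerators and denominators, not the trial record or safety oversight.

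The effect is probably small. Eligibility is confirmed before randomization, the illustration rests on one assumed exclusion, and its striking case has a 2% chance if exclusion is unrelated to the event. This is also a pilot with descriptive safety tables. All of that is accepted, and it limits the size of the point without making 20.c right.

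Finally, the ITT label sits beside its own definition and Section 23 assigns no analysis to an ITT set, so no result depends on the name. That too stands; the label is wrong, but it is a matter of terminology.

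**Conclusion.** The concern holds. Sections 20.c and 22.a define different safety sets, and 23.b does not choose between them. Read literally, 20.c removes exposed subjects from the adverse event tables, which is the wrong rule for a safety population and not merely missing detail. The ITT label misdescribes a set that requires eligibility and dosing.

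The effect is zero if no dosed subject is later found ineligible. It is one subject in the denominator for each such case, and at most that subject's events in the numerators. With one exclusion in an arm of 50, a row with a single event can change from 1/50 to 0/49, or only from 1/50 to 1/49. These figures rest on an assumed exclusion, because the documents give no rate. The definition should be fixed before the tables are programmed; nothing here suggests that the trial's results would be invalidated.

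**What to change.** In 20.c, delete the eligibility condition, so that the safety population is all subjects who apply at least one dose, analysed by treatment received. Remove the ITT label from this set; if the term is wanted, reserve it for all randomized subjects analysed as randomized. In 23.b, state that the adverse event tables use the safety population. Keep eligibility as a condition of the PP set in 20.a.

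Only deleting the eligibility condition and naming the set in 23.b are needed to resolve the conflict. Specifying treatment received and reserving ITT are ordinary good practice that can be added in the same edit. The cost is wording in two sections, with no new data. If the eligibility phrase was only shorthand for enrolled subjects, the tables do not change.
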